### **Other Clinical Assessments**

**a. Pulmonary Function:** Pulmonary function testing will determine the FEV1, with testing performed according to ATS guidelines (79). We anticipate no meaningful change in FEV1 during the course of the study, but we will confirm this by measuring spirometry at each study visit. Both sites will use a portable spirometer (nSpire Health, Inc.). Data will be presented in absolute numbers and as percent of reference predicted values, using prediction equations from Hankinson (95).

#### Contraindications for PFT:

Pulmonary function testing will not be performed in subjects within 3 months following a myocardial infarction, diagnosis of an abnormal heart rhythm, abdominal or thoracic surgery, brain, ear, eye or ENT surgery, unstable angina, or oral or facial pain that could be exacerbated by a mouthpiece. PFT will not be performed if heart rate is < 40 or > 120. These conditions will be assessed with a screening questionnaire and measurement of heart rate.

#### Withholding of Usual Bronchodilator Therapy:

For this study, subjects are not asked to withhold their bronchodilators.

#### Post Bronchodilator Spirometry Testing:

Albuterol 2 puffs will be used. Subjects will be asked about time of most recent use, past allergic reaction or problems to taking albuterol, and about a history of a cardiac arrhythmia. Any positive response will require the PI or covering physician to decide whether to proceed with administration of albuterol. After administration of albuterol, the subject will be asked if they have any new symptoms. If there are questions, the PI or covering provider will assess further.

The screening form will be administered by the RA. If the participant answers no to all questions, the RA will administer albuterol. When needed as directed by the safety form, the study provider will assess the participant, either in person or by telephone. If the decision is made by the study provider to administer albuterol, then an on-site provider will be notified. On-site providers include [name], [name], [name], [name], [name], [name], PA, and Pulmonary Fellow on call. There is a Pulmonary Section Impact Form in place. The study provider will complete a form documenting approval to administer albuterol or not.

We maintain a Drug Control, Storage, and Tracking log for Albuterol with columns for date and patient ID, study visit number, drug source, lot numbers, and their expiration dates.

Albuterol will be obtained from the VA pharmacy. We will use one canister of albuterol until it is depleted of medication, and we will use a single-use spacer with a one-way valve for each participant.

**b. Depression:** Depression will be assessed with the 24-item Beck Depression Inventory (96). Patients with a Beck total score  $\geq 14$  will, with the patient's permission, have their primary healthcare providers informed of the results, with the suggestion that they might consider referral for evaluation and/or treatment of depression. Additionally, the PI will be notified if participants report suicidal thoughts on question 9 of the Beck's, and the PI will evaluate the patient for need for referral to the ER for further evaluation and treatment.

**c. Physical Activity Questionnaires** (Appendix 2): We will use the community healthy activities model program for seniors (CHAMPS) Physical Activity Questionnaire (97). The CHAMPS is a 41-item instrument validated in the elderly, which assesses PA information from several domains including leisure, household, and occupational. Frequency and total time spent per week allows estimation of caloric expenditure. In addition, we will use a Physical Activity Recall checklist developed by [name] to measure free-living PA specifically in patients with COPD (20). A higher number of daily activities performed is associated with better indices of COPD status, including higher FEV1 and lower BODE index (20).

**d. COPD Knowledge:** The Bristol Knowledge Questionnaire will be used to test what patients learn and understand about COPD. The 65 items require 10-20 minutes to complete and cover topics such as symptoms, exacerbations, smoking, vaccination, and medication use. It has demonstrated internal consistency, validity and reliability.

**e. Exercise Self Efficacy:** The belief in one's ability to self-regulate and exercise regularly when faced with challenges is a key variable that influences exercise adherence. The Exercise Self-Regulatory Efficacy Scale (Ex-SRES) for persons with COPD will be used to measure exercise self-regulation. The Ex-SRES incorporates items from Resnick's self-efficacy scale for older adults and McCauley's self-efficacy questionnaire for sedentary adults. The 16-item questionnaire has been shown to be reliable and valid in COPD.

**f. Sleepiness:** Epworth Sleepiness Scale

**g. Social Support:** MOS Social Support Survey

**h. Diet:** Dietary Questionnaire

**i. Pain:** Brief Pain Inventory

### **Monitoring for Adverse Events (AdEs)**

We have convened an independent, external Data and Safety Monitoring Board (DSMB) to review recruitment, follow-up rates, protocol adherence, and safety results. The DSMB is composed of [name], an expert in pulmonary rehabilitation and COPD clinical trials and pulmonologist at Boston Medical Center, [name]. an expert in telemedicine methods in COPD at Southern California Kaiser Permanente, and [name], PhD, NP an expert in patient-centered coaching and behavioral change methodologies and interventions in persons with COPD at Touro University of California. They will meet every 6 months, and as needed, by telephone conference. They will monitor the number of adverse events (AdEs) and serious adverse events (SAEs) and unanticipated problems between the 2 arms of the study.

Although the proposed study presents minimal risk, there is the potential for AdEs related to increased walking and exercise. Based upon our pilot study with ESC, the most common SAE will be hospitalizations for a COPD exacerbation, which are unrelated to the exercise intervention.

The most common AdEs will be musculoskeletal injuries. In order to minimize risk, subjects will be enrolled in the study only if they have medical clearance from their healthcare provider. In addition, subjects will be screened for clinically active cardiovascular disease (such as angina or decompensated congestive heart failure) and exercise-induced hypoxemia as part of baseline testing. Subjects in both arms will be instructed to notify their healthcare provider if they experience any change in their clinical condition, and to notify study staff of any change in medications, urgent care visits, emergency room visits, or hospitalizations. During the study, subjects will be regularly monitored for adverse effects of exercise during clinic visits and telephone contacts. In addition, participants can report adverse events (AdEs) by telephone at any time. The PI will contact participants by telephone if any reported AdE suggests clinical deterioration warranting immediate medical attention. All SAEs and unanticipated problems will be reported to the respective IRBs at the time of continuing review, but would be reported to the study DSMB immediately. If an event is possibly, probably or definitely related to the intervention, it will be classified as intervention-related.

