The study uses a website created and maintained by [name] and her staff at the University of Michigan. They have no direct contact with any study participants. After the account is created, participants access the website using their unique username and password. Participants will upload step-count data to the website over the Internet. These data are stored on a study server on a secure network behind the firewalls of the University of Michigan. Per policies of the University of Michigan, the website is secured, the study server is located on a secured network, and data are backed up at regular intervals. The data stored on the study server are: unique study ID, username and password, and step count numbers. No protected health information (PHI) will be stored on the study server. The UMich server does not track IP addresses. A Data Use Agreement between the University of Michigan and VABoston and VABirmingham will be executed before the study starts.

In addition, test results from this research study as well as hospitalization records, laboratory test results, and radiology reports from care provided outside of the VA may be disclosed to [name] and his research staff at the VA Birmingham, and to the members of the Data and Safety Monitoring Board who oversee this study. This information would be associated only with the participant's unique study ID.

Removal of access to research study data will be accomplished for study personnel when they are no longer part of the research team.

In accordance with VA Policy, procedures are in place for reporting incidents. All incidents will be reported immediately to the PI, the VA Boston Information Security Officers and Privacy Officers, and to the VA Boston Institutional Review Board.

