During the study, subjects will be regularly monitored for adverse effects of exercise during clinic visits and telephone contacts. In addition, participants can report adverse events (AdEs) by telephone at any time. The PI will contact participants by telephone if any reported AdE suggests clinical deterioration warranting immediate medical attention. Subjects in both arms will be instructed to notify study staff if they experience any change in their clinical condition, any change in medications, or have urgent care visits, emergency room visits, or hospitalizations. During the study, if a subject experiences a medical problem that prevents walking and exercise, he will be temporarily suspended from the study and will resume when at baseline clinical status. Any AdEs that are immediately life-threatening, cause permanent or lasting harm, or require a hospitalization will receive a serious classification. All serious adverse events (SAE) and unanticipated problems will be reported to the respective IRB at continuing review but reported to the study DSMB immediately. If an event is possibly, probably or definitely related to the intervention, it will be classified as intervention-related. Based upon our prior experience, the most common SAE will be hospitalization for a COPD exacerbation. The most common AdE will be musculoskeletal injuries.

We have convened an independent, external Data and Safety Monitoring Board (DSMB). They will monitor the rates of AdEs and SAEs and unanticipated problems between the 2 arms of the study. The DSMB is composed of [name] an expert in pulmonary rehabilitation and COPD clinical trials at Boston Medical Center, [name] an expert in telemedicine methods in COPD at Southern California Kaiser Permanente, and [name], PhD, NP an expert in patient-centered coaching and behavioral change methodologies and

interventions in persons with COPD at Touro University of California. They will meet every 6 months, and as needed, by telephone conference.

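### SAEs and unanticipated problems go to the DSMB at once but to the IRBs only at continuing review, with no earlier IRB route for any subset and no stated route from the DSMB to the IRBs

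*Combined protocol and SAP*

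**What the plan says.** The rule appears twice. Monitoring for Adverse Events (AdEs) states "All SAEs and unanticipated problems will be reported to the respective IRBs at the time of continuing review", and the sentence continues "but would be reported to the study DSMB immediately". Section (b) Protection Against Risks, in the Human Studies section, has the same pair of timings: SAEs and unanticipated problems "will be reported to the respective IRB at continuing review but reported to the study DSMB immediately".

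Both sections then label any event with at least a possible relation to the intervention as intervention-related. Neither attaches a reporting consequence to that label.

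On the DSMB, the plan says "They will monitor the number of adverse events (AdEs) and serious adverse events (SAEs) and unanticipated problems between the 2 arms of the study" and "They will meet every 6 months, and as needed, by telephone conference". It states no trigger for an unscheduled meeting, no criteria for pausing enrolment and no duty to inform the IRBs.

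The Information Security section deals with a separate class of event: "All incidents will be reported immediately to the PI", with the security and privacy officers and the VA Boston IRB as the other recipients.

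**The concern.** The rule treats all events alike. An expected admission for a COPD exacerbation and an unexpected serious event judged definitely related to the walking programme reach the IRBs at the same time, namely the next continuing review. The plan says nowhere that a concern raised by the DSMB reaches the IRBs sooner.

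The DSMB and the IRBs do different jobs. By the plan's own description, the DSMB monitors recruitment, follow-up, adherence and event numbers by arm. It is given no task concerning the consent information. If a new risk came to light, consent at both sites could continue on unchanged information until the IRBs next looked. Recruitment runs for 30 months and each participant stays for up to 13, so the delay could affect people already enrolled as well as new entrants.

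**Working it through.** No sample size, power or event figure in the plan bears on this point, so there is no stated figure to reproduce. The check is a comparison of the texts, followed by a simple count of how many people could enter during the delay.

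**Texts side by side**

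| Event | DSMB | IRBs | Where stated |
|---|---|---|---|
| Any SAE, related or not | Immediately | Continuing review | Monitoring for Adverse Events; Protection Against Risks |
| Any unanticipated problem | Immediately | Continuing review | Same two sections |
| SAE labelled intervention-related | Immediately (as any SAE) | Continuing review (as any SAE) | Same two sections; the label changes nothing |
| DSMB safety concern | Originates there | No route stated | – |
| Data-security incident | Not mentioned | Immediately, VA Boston IRB only | Information Security |

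The two sections on adverse events agree with each other, so this is a rule and not a slip or a gap. The last row shows that a prompt channel to one IRB already exists. It covers a different class of event.

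**People entering between two continuing reviews**

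Inputs:
- Rate: 3-4 per site per month (timetable in Work Proposed; Recruitment and Informed Consent).
- Sites: 2.
- Randomisation target: 185 over 30 months.
- Review interval: not in the documents. I assume 6 or 12 months, for illustration only.

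Formula: largest number entering = sites × monthly rate per site × interval. This is the case where the event falls just after a review.

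- Monthly entry: 2 × 3 = 6 to 2 × 4 = 8.
- 6-month interval: 6 × 6 = 36 to 8 × 6 = 48.
- 12-month interval: 6 × 12 = 72 to 8 × 12 = 96.

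If the event is equally likely at any time in the interval, the average is half of these: 18-24 and 36-48.

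On the randomisation target the rate is 185 / 30 = 6.17 per month, which gives 6.17 × 6 = 37 and 6.17 × 12 = 74.

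The plan's figures for people enrolled before randomisation differ: 240 in Sources of Materials and 320 in the timetable. Spread over 30 months they give 240 / 30 = 8 and 320 / 30 = 10.7 per month, that is 48-64 over 6 months and 96-128 over 12. The 3-4 per site rate is therefore not a high choice.

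**The case against.** The strongest reply is that independent review is not delayed at all. An external board receives every SAE and unanticipated problem immediately, can meet as needed and compares the arms. That stands. A reader who saw only the first half of the sentence might infer that new risks can go unreviewed while people keep enrolling. The documents do not support that reading: what is deferred is IRB review.

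A reader might also infer that the plan contradicts itself, because data incidents reach an IRB at once and clinical events do not. It does not. The Information Security sentence concerns another class of event, has its own recipients and names only the VA Boston IRB. Two timelines for two classes of event are compatible. The sentence shows only that prompt reporting to an IRB is feasible in this study.

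Nor can it be concluded that the timing breaches a regulation or VA policy, since the documents do not give those rules. Local policy may well require faster reporting whatever the protocol says. It also cannot be claimed that participants were not told of a given risk: the plan does not define an unanticipated problem, and the consent pages are not available here.

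The other safeguards are real. Medical clearance is required, the investigator telephones participants whose reported events suggest deterioration, and the teams are in daily email contact with calls every other week. That contact is described as serving consistent data collection, and none of these measures brings an event to an IRB.

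Finally, the plan regards the study as minimal risk, the counts depend on an assumed interval, and under 1:1 allocation only about half of those randomised receive the web programme. All of this limits the size of the point. The control arm, however, is also told to increase walking and undergoes the same tests, and consent information concerns every entrant.

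**Conclusion.** The point holds as a limited and inexpensive improvement in participant protection. Safety review by the DSMB is prompt. IRB review of a new risk, and of what participants are told about it, can lag until continuing review, with no exception for unanticipated or intervention-related events and no stated path from the DSMB to the IRBs.

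The size is illustrative: up to 36-48 people entering between reviews at a 6-month interval and up to 72-96 at 12 months, or 37 and 74 on the randomisation target. These figures assume the interval and recruitment at the planned rate. They matter only if an event arises that would change the IRBs' view and the DSMB does not itself bring about a pause or inform them. The finding does not touch the validity of the primary analysis.

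**What to change.** In both Monitoring for Adverse Events and Protection Against Risks:

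1. Send unanticipated problems, and SAEs that are both unexpected and at least possibly intervention-related, to both sites' IRBs at the same time as the DSMB report. Define unexpected in one line, for instance by reference to the plan's own list under Potential Risks.
2. Add a sentence that safety concerns raised by the DSMB are forwarded to both IRBs.
3. Keep continuing review for the summary of expected or unrelated SAEs, so that the IRBs are not sent each COPD admission singly.

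Stating the continuing-review interval would let a reader judge the remaining delay. The cost is a few sentences and a small added reporting workload, since the report to the DSMB is already required. Design, sample size and participants' care do not change.

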### Assessment of Treatment Fidelity

To promote treatment fidelity in both groups, study staff will review instructions to slowly and steadily increase walking and exercise with participants every 3 months (98). To measure treatment fidelity in both groups, subjects will complete daily exercise logs (98). The exercise log is intentionally simple to minimize its potential influence to be part of the intervention (Appendix 2). Subjects circle a yes/no response to three questions about whether exercise was performed that day. Subjects will return the logs by mail to study staff every month, and review them in person every 3 months. Compliance with treatment in both arms will be defined as having >70% of days (~5 out of 7 days/week) with exercise. We propose an intention-to-treat analysis since the reasons for noncompliance may be related to COPD severity. Thus, all subjects will be analyzed and not excluded based on compliance. As a sensitivity analysis, however, we will examine 6MWT distance and secondary outcomes on a per-protocol basis, where noncompliant subjects ( $\geq 30\%$  of days with no exercise performed on logs) from each treatment arm will be excluded from the analysis (Table 2).

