Using a standardized script at the randomization phone call, study staff will deliver verbal instructions to all subjects to encourage participants to increase one's walking slowly and steadily, and to increase the amount of exercise each week. Exercise is defined as planned PA in addition to activities performed as part of one's daily routine. Daily PA is all PA performed, including exercise. Increasing daily PA and exercise are goals of the program. Exercise can be mainly walking in the community or using exercise equipment at a local gym. We intentionally do not specify duration or intensity of exercise both to mirror usual care and to avoid any confusion with walking goals instructed by the WEB intervention. Adapted written materials from [name] (on our DSMB), which are currently used at the University of Washington and VA Boston, reinforce the verbal instructions. All subjects will receive this 42-page booklet (Appendix 1) with information about cardiovascular endurance and strengthening exercises, an action plan for identifying symptoms of a COPD AE, and how to resume exercise after a COPD AE. The written booklet also contains information about oxygen use during exercise and available resources for smoking cessation. To enhance treatment fidelity (see D.8) and to measure compliance with the study, subjects will receive exercise logs in which they will track whether they exercised each day (Appendix 2). The next instance that participant will have contact with study staff will be at a clinic visit 3 months following the baseline visit.

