
To objectively measure engagement in PA, the pedometer will directly measure 14 days of walking of subjects in both arms. To assess treatment fidelity, exercise logs will be collected from subjects each month. Participants will be contacted by telephone at month 9. They will provide an interim history of home exercise and answer questions about symptoms, medications, AEs, and hospitalizations that occurred during the prior 3 months. Subjects will also receive a mailing with questionnaires (Barriers to Exercise, Physical Activity Recall, SGRQ, VR-36, UCSD SOB, Bristol's COPD Knowledge, Exercise Self-Efficacy, CHAMPS Physical Activity, Beck Depression Inventory, and Exercise Logs) to complete at home. At any time, if a subject experiences a medical problem that prevents walking and exercise, s/he will be suspended from the study. S/he will resume the study when s/he has returned to baseline clinical status.

It is expected that some subjects may be unable to complete all the proposed assessments during the study visits. Furthermore, subjects may refuse to complete any portion of the study assessments.

**Table 5:** Schedule of Clinic Visits (C), Telephone Calls (P), and Assessments (both study arms)

	Baseline C00	Month 3 C03	Month 6 C06	Month 9 P09	Month 12 C12
Medical and Exercise History	X	X	X	X	X
6-Minute Walk Test	X	X	X		X
Barriers to Exercise Questionnaire	X	X	X	X	X
Physical Activity Recall Questionnaire	X	X	X	X	X
HRQL SGRQ	X	X	X	X	X

Veterans SF-36 HRQL	X	X	X	X	X
MOS Social Support Questionnaire	X	X	X		X
MMRC	X	X	X		X
UCSD SOB	X	X	X	X	X
Spirometry	X	X	X		X
Blood Draw for Biomarkers	X	X	X		X
Beck Depression Inventory	X	X	X	X	X
CHAMPS Physical Activity Questionnaires	X	X	X	X	X
Bristol's COPD Knowledge	X	X	X	X	X
Exercise Self Efficacy	X	X	X	X	X
Epworth Sleepiness Scale	X	X	X		X
Brief Pain Inventory (Short form)	X	X	X		X
Intervention Feedback Questionnaire (Intervention arm only)			X		X
Dietary Questionnaire	X				X
Exacerbation, Adverse Event Monitoring, and Hospitalization History	X	X	X	X	X
Daily Exercise Logs	X	X	X	X	X
Daily Step Count	X	X	X	X	X
DXA Scan (VABoston site only)*	X				X
Body Composition/Bioimpedance (VABoston site only)	X**				X**

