### **Statistics (power analysis)**

Prior to analyzing the outcomes, we will summarize and compare baseline demographic and clinical variables by treatment group. Any unbalanced characteristics occurring despite randomization will be assessed as potential confounders in multivariate analyses. Analyses will be performed with the SAS statistical software package (9.3, SAS Institute; Cary, NC).

**Primary Aim:** To determine the efficacy of the WEB intervention to increase 6MWT distance.

We focus on 6MWT distance at 6 months since we predict that the greatest difference in 6MWT distance between study arms will occur at month 6, at the end of the interventional phase. We have revised our statistical analysis plan to use 2-way factor analysis or analysis of variance (ANOVA). This approach will assess the effect of intervention versus control on 6MWT distance, using absolute measures of 6MWT distance at baseline and 6 months. Two-way ANOVA will allow us to assess the effect of treatment (intervention versus control), and additionally allow us to assess the interaction between treatment and time (treatment-time) on 6MWT distance. We will use a mixed model (PROC MIXED in SAS) to perform the 2-way ANOVA given its flexibility of modeling the variances and covariances, its robustness in accounting for correlated data (repeated measures data), and its flexibility in handling missing data. Models will have 6MWT distance as the dependent variable, and treatment, time, and treatment-time as independent variables. In this approach, models will also include study site and any unbalanced baseline characteristics as covariates. Primary analyses to determine the effect of WEB on 6MWT distance will use the intention-to-treat approach to include as many randomized subjects as possible in the analyses. Subjects will be considered to be in his/her randomly assigned arm no matter how much he/she participated in it. As a sensitivity analysis, however, we will examine 6MWT distance on a per-protocol basis, where noncompliant subjects ( $\geq 30\%$  of days with no exercise performed on logs) in each treatment arm will be excluded from the analysis.

**Anticipated Results:** We anticipate that subjects in the intervention group will have significantly higher 6MWT distance than subjects in the control group at 6 months.

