Total number of AEs and COPD-related hospitalizations will be summed over the 12-month study period. Independence of individual AEs will be assured by considering subjects to have experienced a new AE only if they had been off of oral steroids and antibiotics for at least 14 days following the previous AE (86). Given the count data and expected Poisson distribution of number of AEs and hospitalizations, negative binomial regression models (PROC GENMOD) will be used to calculate risk ratios for AE and COPD-related hospitalizations (86). The

multivariate regression model will include number of AEs (or hospitalizations) as the dependent variable, treatment group as the main predictor, as well as study site, number of AEs (or hospitalizations) in the year prior to enrollment, and any unbalanced baseline characteristics.

**Body Composition by DXA Scan:** Body composition and regional fat analysis will be performed at the baseline study visit and the 12-month study visit using standard software available from the manufacturer. For regional fat measurements, the left and right arm cuts pass through the shoulder joints and as close to the body as possible. The leg cuts separate the hands and forearms from the legs, starting with a diagonal cut through the femoral necks. The midline separates the right and left legs. The images obtained from one of our subjects demonstrate the standard cuts that define the arms, legs, and trunk (see figure to the left). These data can be also be used to calculate a waist-hip ratio (i.e., ratio of

central fat to hip fat) in a standardized fashion using the same landmarks as illustrated by the regions defined on the soft-tissue image. The DXA software can be used to define standard waist and hip regions that will allow comparability of these measurements throughout the study. The lower boundary of the central or waist region, which is also referred to as the android region (A, see figure), is the cut through the pelvis at the level of the iliac crests. The upper boundary of the android region extends upwards to 20% of the distance between the pelvis and the top of the shoulders and the lateral boundaries are the arm cuts. The upper boundary of the gynoid region of interest (G, see figure) is the region below the pelvis cut that extends downward from 1.5 times the height of the android region. Lateral boundaries of the gynoid region are the outer leg cuts.

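### The per-protocol exclusion extends to exacerbations and COPD hospitalizations, events that can themselves create the no-exercise days that lead to exclusion, so the per-protocol event ratio is biased

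*Combined protocol and SAP*

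**What the plan says.** All references are to the combined protocol and SAP.

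- **Compliance rule (Assessment of Treatment Fidelity).** "Compliance with treatment in both arms will be defined as having >70% of days (~5 out of 7 days/week) with exercise". It is measured by daily logs kept after randomization: "Subjects circle a yes/no response to three questions about whether exercise was performed that day". The section does not say how days of illness, hospital stay or suspension are scored.
- **Scope of the per-protocol analysis (same section).** "we will examine 6MWT distance and secondary outcomes on a per-protocol basis, where noncompliant subjects" are excluded from each arm. AEs and COPD-related hospitalizations are listed as secondary outcomes, and nothing is carved out for them. The section makes intention to treat the main analysis, on the ground that noncompliance may reflect disease severity.
- **Statistics (power analysis), Primary Aim.** "As a sensitivity analysis, however, we will examine 6MWT distance on a per-protocol basis". The paragraphs on the secondary aims do not mention a per-protocol analysis.
- **Event endpoint (Statistics, Secondary Aims).** "Total number of AEs and COPD-related hospitalizations will be summed over the 12-month study period". The model is negative binomial.
- **Illness interrupts exercise.** D.5 says that "if a subject experiences a medical problem that prevents walking and exercise, s/he will be suspended from the study", and that the subject resumes on return to baseline status. The usual-care booklet, described under Randomization, covers "how to resume exercise after a COPD AE". Minimizing Attrition and Handling Missing Data expects medical problems and temporary suspension to be the leading reason for missing outcome data in both arms.

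**The concern.** A per-protocol set is easiest to interpret when the outcome cannot decide who belongs to it. Here it can. An AE or hospital stay that stops exercise produces log days without exercise, and those days count toward the threshold that removes the person from the analysis of AEs and hospitalizations. This is selection on the outcome. It would operate even if compliance had no effect on AE risk.

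The analysis is meant to show whether the intention-to-treat result is robust. A biased event ratio could make a real effect look fragile, or show a difference where there is none. The plan already sees that noncompliance may reflect severity; for event outcomes the link is more direct, because the event can cause the noncompliance.

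**Working it through.** **1. The plan's own figure.** Statistics (power analysis) expects 106 AEs in 111 subjects over 12 months and a detectable rate ratio of 1.70 at 80% power and 1.85 at 90%. Poisson-regression power with 1:1 allocation, two-sided 0.05 (sidedness is not stated) and reference rate 106/111 is

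power = Φ[(√106 × ln RR − 1.96 × √4) / √(2 + 2/RR)]

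- RR 1.70: (5.463 − 3.920)/1.782 = 0.866, power 80.7%.
- RR 1.85: (6.334 − 3.920)/1.755 = 1.375, power 91.5%.

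Both agree with the plan. I therefore take 106/111 = 0.955 AEs per person-year and a control/WEB ratio of 1.70 as inputs. With equal arms this means 2 × 0.955 × 1.70/2.70 = 1.20 per year in control and 0.71 in WEB.

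**2. What one episode does.** Let p be a person's exercise share on well days, d the days lost per AE and A the number of AEs. If illness days count as no-exercise days over 365 days, the logged share is p × (365 − dA)/365, and the person is kept only if it exceeds 0.70.

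- One 14-day episode is 14/365 = 3.8% of the year. It removes only people with p up to 0.70 × 365/351 = 72.8%.
- One 28-day episode removes people with p up to 0.70 × 365/337 = 75.8%.
- Days needed to fall to 70%, 365 × (1 − 0.70/p): 24 at p = 75%, 46 at 80%, 81 at 90%, 110 at 100%.

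So a single ordinary episode seldom decides the matter. Several episodes, long ones, or a usual share near 70% do.

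**3. Simulation.** From the plan: the rate 0.955, the ratio 1.70 and the 70% cut-off. Assumed: negative binomial dispersion 0.8; p from a beta distribution with mean 0.75 (parameters 6 and 2), independent of AE risk; full cessation for d days per AE; 12 months of logs; 400,000 persons per arm.

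Share kept, by number of AEs (equal compliance):

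| Days lost per AE | no AE | 1 or more | 3 or more |
|---|---|---|---|
| 14 | 67% | 54% | 36% |
| 28 | 67% | 39% | 7% |

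Per-protocol control/WEB ratio:

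| Scenario | True ratio | 14 days | 28 days |
|---|---|---|---|
| Equal compliance, mean 75% | 1.70 | 1.54 | 1.37 |
| WEB 85%, control 70% | 1.70 | 1.29 | 1.01 |
| WEB 70%, control 85% | 1.70 | 1.86 | 1.90 |
| Equal compliance | 1.00 | 0.99 | 1.00 |
| WEB 85%, control 70% | 1.00 | 0.83 | 0.73 |
| WEB 70%, control 85% | 1.00 | 1.20 | 1.37 |

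If suspended days leave the denominator, the ratio stays at 1.70 (run at 14 days, with equal compliance and with WEB higher).

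**4. Sensitivity (true ratio 1.70, equal compliance).**

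- 7 days lost gives 1.63; 42 days gives 1.31.
- Dispersion 1 gives 1.45 to 1.53 at 14 days and 1.33 to 1.37 at 28 days, depending on the spread of p.
- Mean share 90% gives 1.59 at 14 days and 1.40 at 28.
- Pure Poisson counts at 14 days give 1.67, so under equal compliance most of the shrinkage comes from overdispersion. The plan's negative binomial model allows for overdispersion.

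With unequal shares, other plausible settings widen the range to 0.84–1.39 when WEB exercises more and 1.57–2.06 when control does.

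**The case against.** The best defence has four parts.

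- **Suspension may already solve it.** A subject suspended from the study could reasonably be treated as outside the compliance period. If so, the bias disappears. This stands as a possible intention, but no section says it, and the rule as written counts logged days without exemption.
- **The size is assumed.** No section gives the exercise days lost per AE, and the AE definition needs only 3 days of symptoms. At 3 days lost the ratio would be about 1.68. This stands: the size cannot be read from the documents.
- **Impact is limited.** This is a sensitivity analysis of secondary endpoints; intention to treat is the main analysis, and the AE paragraph specifies no per-protocol model. This also stands, and it limits the priority of the point.
- **The sections need not conflict.** A reader might infer that Assessment of Treatment Fidelity and Statistics contradict each other on scope. The documents do not support that: the 6MWT-only sentence sits under the Primary Aim, whose outcome is 6MWT distance. What remains is that the scope for secondary outcomes is stated in one place only.

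**Conclusion.** The point holds as selection on the outcome: as written, the rule lets AEs and hospitalizations influence who is analysed for them. With a true benefit and equal or higher WEB compliance, the ratio shrinks. The plan expects this situation, since it hypothesises benefit and describes WEB as built to encourage compliance. Under equal compliance, 1.70 becomes about 1.5 at 14 days lost per AE and about 1.35 at 28; with WEB more compliant it can reach 1 or cross it.

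Two stronger readings are not supported.

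- A reader might infer that the ratio is always pulled toward 1. It can move away from 1 if controls comply more, or if there is no true effect and compliance differs by arm.
- A reader might infer that the rule removes the people who had events. At 14 days lost, 54% of those with at least one AE are kept, against 67% of those with none. Removal is preferential, not wholesale.

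The figures rest on assumed days lost, exercise shares, dispersion and a 12-month compliance window, and on illness days counting as no-exercise days. The intention-to-treat event analysis is unaffected. The change is worth making but is not critical to the trial's main conclusion.

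**What to change.** In Assessment of Treatment Fidelity, limit the per-protocol sensitivity analysis to 6MWT distance and the non-event secondary outcomes, and state that AEs and COPD-related hospitalizations are analysed by intention to treat only.

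If a per-protocol event analysis is kept, compute the 70% rule only over days outside AE, hospital and suspension periods. Hospitalization dates are already requested at each visit, and AEs are checked against medical and pharmacy records; suspension start and end dates would need to be recorded if they are not already.

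In either case, use the same statement of scope in Assessment of Treatment Fidelity and in the primary and secondary parts of Statistics (power analysis).

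The first option costs one sentence and the loss of one sensitivity analysis of secondary endpoints. The second costs slightly more data work.
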